The study participants will be recruited in two parallel cohorts – pregnant patients and non-pregnant patients. Pregnant patients tend to be healthy and without comorbidities, and the providers (anesthesiologists) that perform the neuraxial procedure tend to have significant experience. Non-pregnant patients tend to require neuraxial access for diagnostic or therapeutic purposes (i.e. not for the relief of labor pains), and therefore have comorbidities. Additionally, these providers (ER, neurology, etc.) tend to do far less of these procedures. Together, these two tracks provide the breadth of neuraxial access and therefore maximally determine early feasibility of this device.

For both pregnant and non-pregnant patients, the study procedure is the same. Eligible patients will be identified by chart review of various elements of the electronic medical record, as follows:

Labor & Delivery: Patients will be identified in communication with the OB anesthesia team that maintains an “electronic tracking board” in the interdisciplinary workroom in Prentice. Only patients early in labor, who are in relatively low amounts of pain and distress, will be approached by OB Anesthesia research nurses about the study. If the patient agrees to participate in the study she will be randomized that time to one of the three arms (palpation, US, or VerTouch).

Lumbar Puncture: Patients scheduled to undergo diagnostic or therapeutic lumbar puncture will be identified by appointment schedule and chart review. If a patient is determined to be eligible for the study by the provider responsible for the procedure the patient will be approached once availability of the study team is confirmed. The study team will arrange to be present for the procedure at the scheduled appointment time. The proceduralist or study team member will consent the patient, and if the patient agrees to participate in the study he/she will be randomized that time to one of the three arms (palpation, US, or VerTouch).

Randomization:

Prospective, randomized, controlled, observer blinded trial in patients undergoing neuraxial procedures for diagnostic, therapeutic, primary surgical anesthesia or labor pain management.

Group #1: VerTouch utilized for identification of site for labor epidural or spinal anesthesia procedure

Group #2: Ultrasound (US) utilized for identification of site for labor epidural or spinal anesthesia procedure

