Group #3: Control group, palpation utilized for identification of site for labor epidural or spinal anesthesia procedure

Group #4: VerTouch utilized for identification of site for lumbar puncture procedure

Group #5: Ultrasound (US) utilized for identification of site for lumbar puncture procedure

Group #6: Control group, palpation utilized for identification of site for lumbar puncture procedure

Participants will be randomized to treatment groups based on a random computer-generated schedule (<https://www.randomizer.org>). Proceduralists will not be blinded to randomization, however blinded research personnel will observe the procedure after site determination and collect all outcome measures in this study.

For groups 1-3, on request of neuraxial procedure the research nurse and proceduralist will proceed to the patient's room with all normal supplies in addition to the VerTouch and US machine designated for this study. The research nurse will then un-blind to proceduralist to the patient's group and site identification will proceed. Regardless of the group, the proceduralist will make a mark at the site identified for the procedure using a chlorhexidine safe surgical marking pen. After completion of marking, the research nurse will notify the observer that they may enter the room to observe the procedure and collect the relevant data. Observers will be limited to 3 observers, and additionally inter-observer variability will be minimized using video corroboration of at least 10 procedures.

If one of the blinded study observers is not readily available due clinical responsibilities, the research nurse will video record the procedure per protocol. The procedure video will be reviewed by the blinded observer and the number of redirections and reinsertions will be counted and relayed to the research nurse for completion of data collection.

For groups 4-6, once the patient is in the procedural suite the proceduralist will be un-blinded. He/she will proceed to mark the patient with the appropriate modality determined by the group number. After marking, the proceduralist will allow the research observer to enter the room to observe the procedure and collect the relevant data. Observers will be limited to 3 observers, and additionally inter-observer variability will be minimized using video corroboration of at least 10 procedures.

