All standard procedures for neuraxial procedures will be followed (standard practice) after site determination including time out, skin prep, hemodynamic monitoring, post-procedure instruction etc.

Zoomed in audio-less video of the procedure sight will be collected during at least 10 of the procedures, at each site, for inter-observer variability determination. If the subject has any identifying marks in or near the procedure site or refuses video capture of the procedure no video or images will not be collected in that subject. If the blinded observer is not present and the procedure cannot be recorded for any of the above reasons, the patient will be removed from the study.

Data collected on the VerTouch device will only be associated with the subject number when collected from device for technical evaluation of pressure sensor performance.

If US is used the provider chooses to save an image of the anatomy visualized the research nurse or staff will save that image under the subject number for post-hoc analysis of anatomy identified and image quality achieved.

DATA AND SPECIMEN BANKING

We will collect and data including reason for procedure, type of procedure, any anatomical issues affecting procedure (including but not limited to: scoliosis, positioning, BMI, paralysis), and age. The video/images collected will allow us to compare the observer variability.

SHARING RESULTS WITH PARTICIPANTS

Results will not be shared with participants.

STUDY TIMELINES

The individual will participate in the study for the duration of the procedure, which is usually approximately half an hour. It will take approximately one year to enroll all participants, and approximately 3 months to perform data analysis.

INCLUSION AND EXCLUSION CRITERIA

Inclusion criteria are any adult patients undergoing a neuraxial procedure. Necessary to this is the inclusion of pregnant women who make up a significant fraction of neuraxial procedures.

Exclusion criteria are those patients who do not speak English, have a plastic allergy, or are unable to consent.

Other special populations (individuals who are not yet adults, prisoners, vulnerable populations) will also be excluded.

If it is impossible to take a photograph that does not include identifying marks on the back (i.e. a birthmark or tattoo) the patient will be excluded from the video portion of the study

VULNERABLE POPULATIONS

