Pregnant women will be included in the study because they make up the primary population that will benefit from the success of this device. As otherwise young and healthy females, they also represent a group that, if a serious adverse effect of neuraxial access were to occur, could result in significantly lifelong morbidity.

The device has been tested on cadavers, 5 healthy subjects to prove sensor function, 8 healthy subjects who did not undergo a procedure to prove limited congruence with palpation, and 10 healthy subjects that did not undergo procedure to prove feasibility of functional design.

At this time the device needs to be tested in a setting where patients are undergoing procedures, and that is the purpose of this study. It is critical that the study contain pregnant women in the population as they receive the highest rate of neuraxial procedures, have significantly different anatomy than the general population and stand to gain the most from the success of the device. If this device were to be successful in identifying the optimum needle placement for epidural placement in pregnant women, this could one day significantly reduce the discomfort and possible side effects of neuraxial procedures in pregnant women. Notably, a relatively large percentage (up to 5%) of women will experience a significant headache after neuraxial access due to “blind” needle guidance. This can be debilitating, especially in the setting of labor and birth. This non-invasive, inexpensive device holds promise to one day reduce this morbidity and therefore significantly improve the experience of these women during the birth of their child.

HRP 412 has been reviewed

PARTICIPANT POPULATION(S)

Accrual Number:	Category/Group: (Adults/Children Special/Vulnerable Populations)	Consented: Maximum Number to be Con- sented or Reviewed/Col- lected/Screened	Enrolled: Number to Complete the Study or Needed to Address the Re- search Question
Local	Pregnant Women	60	60
	Adults	60	60
Study-wide			
Total:		120	120

RECRUITMENT METHODS

Patients will be identified by the anesthesiology team by chart review after the team has been alerted to the need for pain management and approached in person to be recruited.

The source of participants will be Prentice Women's Hospital and NM (Galter, Feinberg, Lavin) pavilions.

COMPENSATION FOR PARTICIPATION IN RESEARCH ACTIVITIES

There will be no compensation for participation.

WITHDRAWAL OF PARTICIPANTS

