Statistical analysis: Data will be compared between groups using the chi2 statistic or the Fisher's exact test. A $P < 0.05$ will be required to reject the null hypothesis.

PROVISIONS TO MONITOR THE DATA TO ENSURE THE SAFETY OF PARTICIPANTS
N/A (minimal risk study)

PROVISIONS TO PROTECT THE PRIVACY INTERESTS OF PARTICIPANTS

Patients in this study, whether undergoing neuraxial access for a disease-state or for the treatment of labor pains, will certainly be under some amount of stress. Having a needle placed into one's back, as is the case for neuraxial procedures, can be stress provoking. Extra care will be taken to approach them during a quiet moment when the clinical team has finished their evaluation. It will be emphasized that in no way will this impact their care, and in fact can help future patients undergo these procedures more quickly and safely to minimize their stress.

COMPENSATION FOR RESEARCH-RELATED INJURY
N/A

ECONOMIC BURDEN TO PARTICIPANTS

There is no cost to the patient to be in this study.

CONSENT PROCESS

Consent will take place in Prentice Women's Hospital 8th floor Labor and Delivery unit at a time mutually convenient to the clinical team, patient, and research team. Subjects will also be recruited from Galter, Lavin and Feinberg pavilions (numerous medical units). They will be offered to contemplate their participation up until 10 minutes prior to the time of their neuraxial procedure (if any less than 10 minutes were available for application of the VerTouch device prior to the clinical procedure, this would risk rushing the clinical procedure). REDcap electronic consent will be utilized to decrease the number of times the paper consent would be touched. Multiple

times throughout the process, the participant will be reminded that this in no way affects their standard of care and that participation can be withdrawn at any time.

NON-ENGLISH SPEAKING PARTICIPANTS

N/A

WAIVER OR ALTERATION OF CONSENT PROCESS

N/A

PROTECTED HEALTH INFORMATION (PHI AND HIPAA)

Does the study involve the creation, use, or disclosure of Protected Personal Health Information?

- Will a HIPAA Authorization be obtained from for all participants? Yes
-
- Name
- Age (years)
- Date of procedure
- Telephone numbers
- Medical Record Numbers
- Email address

QUALIFICATIONS TO CONDUCT RESEARCH AND RESOURCES AVAILABLE

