The PI has 10 plus years clinical research experience. Prentice Women's Hospital cares for over 12,000 women a year for childbirth. Over 90 percent request pain management using Anesthesiology services for epidural catheter placement for pain relief. The research team includes 8 nurse clinicians in the Anesthesia care team who will assist the PI during the study period.

In the event of an inadvertent dural puncture the study team and PI will contact the anesthesiology team to follow up with the subject for the next 5 days to assess for complications.

MULTI-SITE RESEARCH N/A

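### Labor patients are randomised at consent in early labor, before the request that triggers the procedure; a woman who then has no block has no primary endpoint, and the consent ceiling leaves no room to replace her

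*Combined protocol and SAP*

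**What the plan says.** All references are to the combined protocol and SAP.

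- **Approach (PROCEDURES INVOLVED, Labor & Delivery):** "Only patients early in labor, who are in relatively low amounts of pain and distress, will be approached by OB Anesthesia research nurses".
- **Randomisation (same paragraph):** "If the patient agrees to participate in the study she will be randomized that time to one of the three arms".
- **Start of the procedure (PROCEDURES INVOLVED, Randomization, groups 1-3):** "on request of neuraxial procedure the research nurse and proceduralist will proceed to the patient's room". Only then is the group disclosed: "The research nurse will then un-blind to proceduralist".
- **Eligibility (INCLUSION AND EXCLUSION CRITERIA):** "Inclusion criteria are any adult patients undergoing a neuraxial procedure".
- **Primary endpoint (STUDY ENDPOINTS):** the total of needle insertions and redirections, which exists only if a needle is placed.
- **Accrual (PARTICIPANT POPULATION(S)):** for pregnant women, the maximum consented is 60 and the number to complete is 60.
- **Allowance (DATA MANAGEMENT AND CONFIDENTIALITY):** 38 per arm and 114 in total are needed; 120 are planned, 40 per arm, with the surplus held for unspecified exclusions.
- **A different approach time (RECRUITMENT METHODS):** patients are identified by chart review "after the team has been alerted to the need for pain management and approached in person to be recruited".
- **Site uptake (QUALIFICATIONS TO CONDUCT RESEARCH AND RESOURCES AVAILABLE):** "Over 90 percent request pain management using Anesthesiology services for epidural catheter placement for pain relief".

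**The concern.** In the labor cohort, allocation comes before the event that makes a woman clearly eligible. If she delivers first, never asks for a block, or has no neuraxial procedure for another reason, she has been randomised but has no outcome. The protocol does not say whether such a woman is counted, replaced or analysed. The only rules for losing a patient concern a procedure that could be neither observed nor recorded (PROCEDURES INVOLVED) and withdrawal (WITHDRAWAL OF PARTICIPANTS).

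At stake are evaluable patients and a clear analysis set. Each such woman becomes a post-randomisation exclusion and draws on a small allowance already needed for those other losses. The losses are also avoidable, because the documents show no use of the allocation before the bedside reveal.

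**Working it through.** **1. Order of events.** The Labor & Delivery paragraph gives early labor, agreement, then randomisation. The text for groups 1-3 gives request, bedside, disclosure of group, marking, then procedure. Together they place randomisation before the request. The endpoint arises only at the last step.

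**2. The plan's own sample size.** Inputs from DATA MANAGEMENT AND CONFIDENTIALITY: first-insertion success p1 = 0.901 (VerTouch) and p2 = 0.629 (ultrasound), alpha 0.05 (taken as two-sided), power 80%. With pooled variance under the null:

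n = [1.960 × √(2 p̄(1 − p̄)) + 0.842 × √(p1(1 − p1) + p2(1 − p2))]² / (p1 − p2)²

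- p̄ = (0.901 + 0.629)/2 = 0.765, so the first term is 1.960 × √(2 × 0.765 × 0.235) = 1.175.
- √(0.901 × 0.099 + 0.629 × 0.371) = 0.568, so the second term is 0.842 × 0.568 = 0.478.
- n = (1.175 + 0.478)² / 0.272² = 36.9, so 37 per arm. The stated 38 is reproduced to within one patient.

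**3. The allowance.** 120 − 114 = 6 in total, or 40 − 38 = 2 per arm, across both cohorts and all causes of loss.

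**4. Expected loss.** The no-procedure rate d is not given. The range 2% to 10% is an assumption. More than 90% of women at the site request an epidural, so 10% is an upper bound for the site as a whole, not a figure for women who join the trial. With 60 labor patients, the expected loss is 60 × d and the chance that at least one has no endpoint is 1 − (1 − d)^60.

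| d | Expected lost of 60 | Chance of at least one |
|---|---|---|
| 2% | 1.2 | 70% |
| 5% | 3 | 95% |
| 10% | 6 | 99.8% |

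At 10% the expected loss equals the whole allowance, and the binomial chance of losing more than 6 of 60 is 39%. At 5% that chance is 3%.

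**5. Effect on power, VerTouch versus ultrasound.** Assume 20 labor patients per arm (60/3) and loss spread evenly, so that n = 40 − 20d per arm. Power = Φ[(0.272 × √n − 1.175)/0.568].

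| d | n per arm | Power |
|---|---|---|
| 0 | 40 | 83.1% |
| 2% | 39.6 | 82.8% |
| 5% | 39 | 82.2% |
| 10% | 38 | 81.1% |
| 15% | 37 | 80.1% |
| 20% | 36 | 78.9% |

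Power falls below 80% only at rates above the assumed range. These figures use first-insertion success, the measure on which the plan is sized. The primary endpoint is a count, but both need a procedure.

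**6. Chance that an arm drops below the stated 38.** An arm does so if more than 2 of its 20 labor patients are lost: probability 0.323 at 10%, 0.075 at 5% and 0.007 at 2%. For the two arms that set the sample size, 1 − (1 − p)² gives 54%, about 15% and 1%. Adding palpation, 1 − (1 − p)³ gives 69%, 21% and 2%, but palpation did not set the 38. Falling below 38 is also not the same as losing the planned power, since 37 still gives 80.1%.

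**The case against.** **The gap may be short.** RECRUITMENT METHODS has patients approached once the team knows that pain management is needed, and STUDY TIMELINES limits participation to the procedure, about half an hour. If those sections govern, fewer women would be lost. This stands as a reason not to assume a long interval, and the documents state no length. It does not remove the point: knowing of a need is not a request for a block, and the Labor & Delivery paragraph is the explicit rule on when to randomise.

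**The loss rate is unknown.** Women who agree to a trial of a neuraxial device may request a block more often than the site as a whole. This stands, and it is why 10% is used only as an upper end.

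**The power effect is small.** This stands: about two percentage points at the upper end.

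**A reader might infer bias from drop-out that depends on arm.** The documents do not support that. The proceduralist learns the group only after the request, and no section says the patient is told sooner. Loss before that step would cost numbers without favouring an arm.

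**A reader might also infer that consent stays open after allocation**, from the sentence "They will be offered to contemplate their participation up until 10 minutes prior to the time of their neuraxial procedure". It sits under CONSENT PROCESS and reads more naturally as time to decide whether to join; a woman who decides late would be randomised late. Withdrawal has its own section.

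**Another remedy exists.** A replacement rule, a defined analysis set and a higher ceiling would deal with the loss without moving randomisation. That would work, but it keeps the post-randomisation exclusions that the later draw largely prevents.

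**Conclusion.** The point holds as a flaw in the timing of randomisation for the labor cohort. Following the plan as written creates avoidable losses after allocation, with no rule for handling them and a ceiling of 60 consented for 60 to complete. Under the assumed 2% to 10% rate, 1 to 6 evaluable patients are expected to be lost from an allowance of 6 that must also cover unobserved, unrecorded procedures and withdrawals. Power for VerTouch versus ultrasound falls from about 83% to no lower than about 81%, before those other losses.

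This rests on an assumed loss rate, 20 labor patients per arm, and the Labor & Delivery paragraph governing when women are approached. That some women will be lost is an inference, though a likely one with 60 patients. The documents do not show a serious loss of power or bias between arms. The lumbar puncture cohort is much less exposed, because those patients already have a scheduled procedure. The change is worth making because it costs very little, not because the trial fails without it.

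**What to change.** 1. **PROCEDURES INVOLVED, Labor & Delivery:** keep consent in early labor, but randomise when the neuraxial procedure is requested and the research nurse is at the bedside, just before the group is disclosed to the proceduralist.
2. **Sample size text:** state that the 120 are counted at randomisation.
3. **PARTICIPANT POPULATION(S):** set the maximum consented for pregnant women above 60, so that consented women who have no procedure are replaced before allocation. For scale, at an assumed 10% no-procedure rate, 60/0.90 = 66.7, so about 67 consents would yield 60 randomised.
4. **RECRUITMENT METHODS and Labor & Delivery:** give one approach time in both places.

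The cost is a wording amendment and a higher consent ceiling. The number randomised stays at 120. The small downsides are that the nurse must draw the allocation at the bedside, where she already discloses it, and that some women will consent and never be randomised.

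### Allocation concealment is not described: no list holder or release step is named, and recruiting roles overlap with those that operate or disclose the arm

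*Combined protocol and SAP*

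**What the plan says.** All of the relevant text is in the protocol under Procedures Involved.

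- **Lumbar Puncture paragraph.** The operator is the gatekeeper: "If a patient is determined to be eligible for the study by the provider responsible for the procedure", the patient is approached once the study team is known to be available. Then "The proceduralist or study team member will consent the patient, and if the patient agrees to participate in the study he/she will be randomized" on that occasion.
- **Labor & Delivery paragraph.** Patients early in labor and in little distress "will be approached by OB Anesthesia research nurses about the study", and a patient who agrees is randomized then.
- **Randomization paragraphs.** "Participants will be randomized to treatment groups based on a random computer-generated schedule", with randomizer.org given as the generator. On blinding: "Proceduralists will not be blinded to randomization, however blinded research personnel will observe the procedure after site determination".
- **Disclosure of the arm.** For groups 1-3 a research nurse tells the proceduralist the group at the bedside. For groups 4-6, "once the patient is in the procedural suite the proceduralist will be un-blinded"; the person who does this is not named.

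The plan does not say who generates or keeps the schedule, how an assignment is released, whether the schedule is blocked or stratified, or that recruiters have no access to it.

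**The concern.** Randomization protects against selection only if those who decide whether a patient enters cannot know or predict the next assignment. Placing randomization after consent is not enough if the next line of the list is already visible to the person choosing whom to approach.

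The stakes are real in this trial. The primary endpoint is the total of needle insertions and redirections. The plan itself lists scoliosis, positioning, BMI and paralysis as features that affect the procedure (Data and Specimen Banking), and several of these can be known before a patient is approached. Any adult having a neuraxial procedure may enter, subject to a few exclusions, and approach is discretionary. The operators are unblinded and the device maker funds the study. An imbalance created at entry would be carried into the comparison, and the blinded observer, who arrives after the site is marked, could not correct it.

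**Working it through.** **1. Who does what, by cohort**

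| Step | Lumbar puncture | Labor |
|---|---|---|
| Identify or judge eligible | Provider responsible for the procedure | Identified with the OB anesthesia team |
| Approach | Once study team is available; person not named | Research nurses |
| Take consent | Proceduralist or study team member | Person not named |
| Draw the assignment | Person not named | Person not named |
| Tell the operator the arm | In the suite; person not named | Research nurse, at the bedside |
| Perform | Proceduralist, unblinded | Proceduralist, unblinded |

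In lumbar puncture, one person may judge eligibility, take consent and operate. In labor, one role both approaches patients and discloses the arm, though the text does not say that the same individual nurse does both. In neither cohort is the draw assigned to anyone.

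**2. What concealment needs, and what is stated**

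- Sequence generation: stated, and not shown to be defective.
- Custody of the list by someone outside recruitment: not stated.
- Release only after entry is fixed: order stated (agreement, then randomization), mechanism not stated.
- Unpredictability of the next assignment: not assessable, because no block sizes are given.

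**3. Predictability without sight of the list**

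A recruiter may know past assignments without seeing the list. Suppose he or she always guesses the arm with most places left in the block. Block sizes here are assumptions.

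- Blocks of 3: (1/3 + 1/2 + 1)/3 = 0.611, so 61% correct.
- Blocks of 6: 56% correct (simulation).
- One list of 60 balanced 20:20:20: 43% correct (simulation).
- Pure chance with three arms: 1/3 = 33%.
- Open view of the list: 100%.

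These are rates of correct guessing, not estimates of bias. They show why custody matters most and why block sizes should be withheld as well.

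**4. Room for selection**

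The labor cohort needs 60 women (Participant Population(s)) over about one year (Study Timelines). The hospital reports over 12,000 neuraxial procedures a year (Significance). 60/12,000 = 0.5%, so at most about 1 in 200 would be enrolled, before allowing for ineligible patients. No screening log is described.

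**5. Sample size**

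The plan gives 38 per group for 90.1% versus 62.9% (Data Management and Confidentiality). Assuming a two-sided 5% test and 80% power, with pooled rate 0.765:

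n = [1.960 × √(2 × 0.765 × 0.235) + 0.842 × √(0.901 × 0.099 + 0.629 × 0.371)]² / 0.272² = 36.9, or 37.

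This is within one patient of the stated 38. The figure does not depend on how allocation is concealed, so neither the gap nor the fix alters it.

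**The case against.** The strongest reply is that this is an omission, and that some readers will make more of it than the text allows. Four stronger readings are tempting.

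- *A recruiter holds the list.* A reader might infer this because the same roles recruit and then operate or disclose. No sentence says so. The order given is eligibility, approach, consent, randomization, and the lumbar-puncture operator learns the arm later, in the suite.
- *The Lumbar Puncture and Randomization paragraphs contradict each other.* They do not. A patient can be randomized at consent and the arm disclosed to the operator afterwards; the labor text sets out the same sequence.
- *A web generator exposes the list.* A publicly available generator does not make the generated list public. That the list was made in advance is a fair reading of the word schedule, but it is not stated.
- *The bias can be sized by supposing some number of swapped patients.* No rate of steering can be drawn from the documents. At the planned VerTouch rate, 40 patients would have only 0.099 × 40 = 3.96 expected failures, so supposing even four converted failures would remove essentially all of them.

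It is also fair that candidates come from an appointment schedule and a tracking board, so a source denominator exists, and that recorded anatomical features would allow some check of balance.

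All of this stands, and it limits the claim. It does not supply the missing safeguard. Later disclosure to the operator protects only that patient's assignment, and only if the consenting operator has not seen it already. It says nothing about custody of the assignments still to come. A balance check detects some steering after the fact but does not prevent it.

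**Conclusion.** The point holds as a gap in allocation concealment, made more serious by role overlap that the documents do record. The plan gives a schedule but no independent holder, concealed release or block policy. Recruiting roles overlap with operating (lumbar puncture) or with disclosing the arm (labor), so entry could depend on the next assignment without breaching anything written. The documents do not show that it would.

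The size of any bias cannot be estimated. The conclusion rests on two things: the randomization text is present and ends without these provisions, and nothing elsewhere in the protocol supplies them. It should be settled before the first patient is enrolled, because concealment cannot be restored afterwards.

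**What to change.** Amend the Labor & Delivery, Lumbar Puncture and Randomization paragraphs of Procedures Involved as follows.

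- A person who neither enrols nor treats patients prepares a separate list for each cohort. Any block sizes are withheld from recruiters.
- The list is loaded in the randomization module of REDCap, which the trial already uses for data and electronic consent. The documents do not confirm that the module is available; if it is not, use sequentially numbered opaque sealed envelopes.
- Each allocation is released, with a time stamp, only after eligibility and consent are recorded.
- The proceduralist learns the group only at the un-blinding step already described, even when he or she took consent.

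The cost is a wording change and a small set-up effort. It adds no patients or procedures and leaves the planned 120 unchanged.
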